9.4.3 Electrocardiogram

For the following ECG measurements during the TE period for Part A for OL-SS for Part A, a summary of observed values and change from baseline values will be provided for overall (“Any ELX/TEZ/IVA”) at each visit (in ms): RR interval, PR interval, QT interval, QTcF(QT corrected for HR), QRS duration, and Heart Rate (beats per minute).

The number and percentage of subjects meeting at least 1 threshold analysis criterion during the TE period for Part A for OL-SS for Part A will be summarized for overall (“Any ELX/TEZ/IVA”). The threshold analysis criteria are provided in Section 12.4.

9.4.4 Vital Signs

For the vital signs measurements during the TE period for Part A for OL-SS for Part A, the observed values and change from baseline values will be summarized for overall (“Any ELX/TEZ/IVA”) at each visit. The following vital signs parameters will be summarized: systolic and diastolic blood pressure (mm Hg), body temperature (°C), pulse rate (beats per minute), and respiratory rate (breaths per minute).

The number and percentage of subjects meeting at least 1 threshold analysis criterion during the TE period for Part A for OL-SS for Part A will be summarized for overall (“Any ELX/TEZ/IVA”). The threshold analysis criteria are provided in Section 12.4.

9.4.5 Pulse Oximetry

For the percent of oxygen saturation measurements using pulse oximetry during the TE period for Part A for OL-SS for Part A, a summary of observed values and change from baseline values will be provided for overall (“Any ELX/TEZ/IVA”) at each visit.

The number and percentage of subjects with shift changes from baseline (normal/missing and low according to the reference range) to the lowest percent of oxygen saturation during the TE Period for Part A for OL-SS for Part A will be summarized for overall (“Any ELX/TEZ/IVA”).

9.4.6 Physical Examination

No tables/figures/listings will be provided for PE data.

9.4.7 Ophthalmology Examination

Ophthalmology examination results will be provided in a data listing.

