^c The Safety Follow-up Visit is required for all subjects. Refer to Section 9.1.2 for subjects who transition to a commercially available or managed access program-supplied next-generation corrector TC regimen. For subjects who complete an ETT Visit 3 weeks or later following the last dose of study drug, the ETT Visit will replace the Safety Follow-up Visit (Section 9.1.3).

^d The Day 1 Visit of this study should be on the same day as the last scheduled visit of the parent study. Subjects whose Day 1 Visit is NOT within 1 day of the last scheduled visit in the Treatment Period of the parent study will have all Day 1 assessments performed (Section 9.1.1). Subjects whose Day 1 Visit is within 1 day of the last scheduled visit in the Treatment Period of the parent study will NOT have to repeat assessments that were performed as part of the last scheduled visit of the parent study Treatment Period.

Table 3-1 VX18-445-110: Treatment Period and Safety Follow-up Visit

| Event/Assessment ^a | Treatment Period | | | | | | | ETT Visit ^b | Safety Follow-up Visit 28 (± 7) Days After Last Dose ^c | Comments |
|--------------------------------------|--------------------|-------------------|-----------------------------------|---|--------------------|-----------------------------|--------------------|------------------------|---|---|
| | Day 1 ^d | Day 15 (± 3 Days) | Weeks 4, 8, 16, 24, 36 (± 5 Days) | Weeks 12, 20, 28, 32, 40, 44, 52, 56, 64, 68, 76, 80, 88, 92 (± 5 Days) | Week 48 (± 5 Days) | Weeks 60, 72, 84 (± 5 Days) | Week 96 (± 5 Days) | | | |
| OE | | | | | X | | X | X | | Subjects <18 years of age on the date of informed consent in the parent study will have an OE within 28 days of the Week 48 and Week 96 Visits. In addition, an OE will be performed within 28 days of the ETT Visit for subjects whose cumulative study drug exposure (in the parent study and current study) is at least 12 weeks since their last study OE. (Section 11.6.6) |
| Complete physical examination | X | | | | | | X | X | | Section 11.6.3 |
| Pregnancy test (all female subjects) | Urine | | Urine | Urine | Urine | Urine | Serum | Serum | Serum | At telephone contact visits, a urine pregnancy test will be performed with a home kit provided by the study site (Section 11.6.2) |
| Serum FSH | | | | | | | | | | As needed for any suspected postmenopausal female with at least 12 months of continuous spontaneous amenorrhea (Section 11.6.2) |

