| | Day 1 ^d | Day 15 (± 3 Days) | Weeks 4, 8, 16, 24, 36 (± 5 Days) | Weeks 12, 20, 28, 32, 40, 44, 52, 56, 64, 68, 76, 80, 88, 92 (± 5 Days) | Week 48 (± 5 Days) | Weeks 60, 72, 84 (± 5 Days) | Week 96 (± 5 Days) | | | |
| Study drug dosing | Day 1 through evening before Week 96 Visit | | | | | | | | | Section 9.6.1 |
| Medications review | Continuous from signing of the ICF through completion of study participation | | | | | | | | | Completion of study participation is defined in Section 9.1.5 |
| Treatments and procedures review | | | | | | | | | | |
| AEs and SAEs | Continuous from signing of the ICF through completion of study participation | | | | | | | | | Sections 13.1.1.3 and 13.1.2.2 |

AE: adverse event; CFQ-R: Cystic Fibrosis Questionnaire-Revised; ETT: Early Termination of Treatment; FSH: follicle-stimulating hormone; ICF: informed consent form; OE: ophthalmologic examination; SAE: serious adverse event; SwCl: sweat chloride; TC: triple combination

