9.1.2 Safety Follow-up

The Safety Follow-up Visit is scheduled to occur 28 (\pm 7) days after the last dose of study drug. The Safety Follow-up Visit assessments are listed in [Table 3-1](#).

The Safety Follow-up Visit is required for all subjects. However, subjects who transition within 28 days of the last dose of study drug to either a commercially available or managed access program-supplied next-generation corrector TC regimen, or to another qualified Vertex study, will complete the Week 96 Visit (or the Early Termination of Treatment [ETT] Visit, if the transition occurs before the Week 96 Visit). In these cases, the Week 96 Visit (or the ETT Visit) will replace the Safety Follow-up Visit.

For subjects who complete an ETT Visit 3 weeks or later following the last dose of study drug, the ETT Visit will replace the Safety Follow-up Visit ([Section 9.1.3](#)).

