9.1.5 Completion of Study Participation

Completion of study participation for each individual subject is defined as: the Safety Follow-up Visit; or, in situations in which the ETT Visit or the Week 96 Visit replace the Safety Follow-up Visit (Section 9.1.2), the ETT Visit or the Week 96 Visit.

If subjects withdraw consent or assent, completion of study participation is defined as date of withdrawal of consent or assent, whichever is earlier (Section 9.9).

If subjects are lost to follow-up (Section 9.1.4), the date of completion of study participation will be defined as the date of last contact.

The end of study is defined in Section 13.2.8.

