9.9 Removal of Subjects

Subjects may withdraw from the study at any time at their own request. Subjects may be withdrawn from study drug treatment at any time at the discretion of the investigator or Vertex for safety, behavior, noncompliance with study procedures, or administrative reasons.

In addition, a subject must be discontinued from study drug treatment if the subject meets any of the following criteria:

- Meets any of the stopping (discontinuation) criteria (Section 9.8)
- Becomes pregnant (Section 11.6.7.2)

If a subject does not return for a scheduled visit, reasonable effort will be made to contact the subject. In any circumstance, reasonable effort will be made to document subject outcome. The investigator will inquire about the reason for withdrawal, request that the subject return all unused investigational product(s), request that the subject return for an ETT Visit and Safety Follow-up Visit, if applicable (see Section 9.1.3), and follow up with the subject regarding any unresolved AEs.

If a subject withdraws consent or assent for the study, no further assessments will be performed. Vertex may retain and continue using the study data and samples after the study ends, and may use the samples and information in the development of the study compounds, for other drugs and diagnostics, in publications and presentations, and for education purposes. If a subject withdraws from the study, the study data and samples collected will remain part of the study. A subject will not be able to request the withdrawal of his or her information from the study data. A subject may request destruction of the samples collected from him or her during the study as long as those samples can be identified as his or her samples.

With the exception of subjects who cannot access the commercial product after regulatory approval because reimbursement by the subject's insurance carrier (whether government or private payer) is not yet available or because the subject lacks insurance coverage, subjects who become eligible to receive commercially available TC by prescription of a physician may be discontinued from study drug dosing and will complete the ETT Visit before beginning commercially available TC dosing. The Safety Follow-up Visit will not be required if the subject immediately continues on commercially available TC.

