11.6.6 Ophthalmologic Examination

OEs are required only for subjects who are <18 years of age on the date of informed consent in the parent study. OEs do not need to be completed if there is documentation of bilateral lens removal for the subject.

All examinations will be conducted by a licensed ophthalmologist or optometrist and will include

- measurement of best-corrected distance visual acuity of each eye; and
- pharmacologically dilated examination of the lens with a slit lamp.

Subjects <18 years of age on the date of informed consent in the parent study are required to complete OEs as indicated in [Table 3-1](#). These examinations should be completed within 28 days of the relevant study visit. An OE is also required within 28 days of the ETT Visit for subjects whose cumulative study drug exposure (in the parent study and current study) is at least 12 weeks since the last study OE.

Any clinically significant abnormal findings will be reported as AEs.

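### A lens finding at a final eye examination done after the Week 96 or ETT Visit can fall outside the TE Period and be seen only in listings

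*SAP*

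**What the plan says.** **Examination.** Under Protocol Table 3-1, subjects under 18 at parent-study consent "will have an OE within 28 days of the Week 48 and Week 96 Visits". An OE is also due within 28 days of an ETT Visit if study drug exposure since the last study OE is at least 12 weeks. Protocol 11.6.6 adds: "These examinations should be completed within 28 days of the relevant study visit". Nothing requires the OE to come before the visit. The same section says: "Any clinically significant abnormal findings will be reported as AEs".

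**End of the TE Period.** SAP 8.2 ends it at the earlier of 28 days after last dose and completion of participation in Part A. Dosing runs "Day 1 through evening before Week 96 Visit" (Protocol Table 3-1).

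**Completion.** Protocol 9.1.2 covers subjects who move, within 28 days of last dose, to commercial or managed-access triple combination or to another qualified sponsor study: "In these cases, the Week 96 Visit (or the ETT Visit) will replace the Safety Follow-up Visit". An ETT Visit 3 weeks or more after last dose also replaces it. For commercial supply, Protocol 9.9 says: "The Safety Follow-up Visit will not be required if the subject immediately continues on commercially available TC". Under Protocol 9.1.5 a subject normally completes at Safety Follow-up. The exception is worded "in situations in which the ETT Visit or the Week 96 Visit replace the Safety Follow-up Visit (Section 9.1.2), the ETT Visit", and it names Week 96 in the same way.

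**Reporting.** AE summary tables cover TEAEs only (Protocol 12.3.4.1, SAP 9.4.1). All AEs, including post-treatment AEs, go into a subject listing (SAP 9.4.1). For the eye examination itself, "Ophthalmology examination results will be provided in a data listing" (SAP 9.4.7).

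**The concern.** The protocol's own OE window extends past the period in which an event can count as treatment-emergent, and neither document says that a late OE belongs to its visit or to the TE Period. A new lens opacity found at a fully compliant OE and dated to it is then, by the SAP 9.4.1 definitions, a post-treatment AE.

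The Week 96 OE matters most. A completer has two scheduled OEs in this study, at Weeks 48 and 96, and only the second reflects the whole 96 weeks. Protocol 9.3.3 includes OEs because eye monitoring is recommended for subjects under 18 on ivacaftor-containing regimens. AEs are part of the primary endpoint (SAP 5.1), so the tables would undercount lens events in the group being monitored for them. No other summary picks them up, because SAP 9.5.1 limits AEs of special interest to transaminase elevations and rash.

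**Working it through.** The documents give no figure for this overlap, so the check is a day count.

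**Inputs.** Day 0 is the last dose. Dosing stops the evening before Week 96, so the Week 96 Visit is day 1. Safety Follow-up (SFU) is at 28 ± 7 days, so days 21 to 35 (Protocol Table 3-1). The latest compliant OE is the visit day + 28.

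**Formulas.** TE end = min(28, completion day). Overrun = latest OE day − TE end.

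| Path | TE end | Latest OE | Overrun |
|---|---|---|---|
| Week 96, SFU on day 28 to 35 | 28 | 29 | 29 − 28 = 1 day |
| Week 96, SFU on day 21 | 21 | 29 | 29 − 21 = 8 days |
| Week 96 replaces SFU | 1 | 29 | 29 − 1 = 28 days |
| ETT on day 7, SFU on day 28 to 35 | 28 | 35 | 35 − 28 = 7 days |
| ETT on day 7, SFU on day 21 | 21 | 35 | 35 − 21 = 14 days |
| ETT on day 7 replaces SFU (transition) | 7 | 35 | 35 − 7 = 28 days |
| ETT on day 21 replaces SFU | 21 | 49 | 49 − 21 = 28 days |

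If the OE may fall on either side of the visit, the window is 28 + 1 + 28 = 57 days. The part outside the TE Period is 28/57 = 49% where Week 96 replaces SFU, 8/57 = 14% with SFU on day 21, and 1/57 = 2% with SFU on day 28 or later. These are shares of calendar days, not of examinations or events.

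**Is the finding recorded as an AE?** Protocol 11.6.6 makes clinically significant OE findings AEs and sets no time limit. Protocol 13.1.1.3 stops AE collection at completion. Where Week 96 replaces SFU, every overrun day falls after completion, so the two rules meet and the documents do not say which prevails. After Safety Follow-up, Protocol 13.1.2.2 asks only for SAEs considered related to study drug, which many lens opacities would not be.

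**Where it appears.** If recorded with the OE date as onset, it is a post-treatment AE: in the AE listing and the OE listing, and in no table. If not recorded as an AE, it is in the OE listing alone.

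**The case against.** A reader might infer that such a cataract appears nowhere except the OE listing. The documents do not support that as a general statement. Protocol 11.6.6 calls for an AE, and SAP 9.4.1 lists post-treatment AEs and gives SAEs a separate listing with a TEAE flag. Only if the site treats AE collection as closed does the OE listing stand alone.

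Detection is also not onset. TEAE status follows the date the event developed, and an opacity seen days after 96 weeks of dosing may have no clear start. Under SAP 9.4.1 an AE with a missing or partial start date and no clear evidence of timing is a TEAE. Under SAP 12.3 a missing day is generally set to the first of the month, which can bring the event back inside the TE Period. This stands: the loss requires a full onset date equal to the OE date, or no AE record.

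The ordinary Week 96 path is hardly touched, with an overrun of 1 day when SFU is on day 28 or later. The SAP describes a two-part study while the supplied protocol has one part, so Part A completion for Part B rollovers cannot be checked. These points also stand.

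Finally, safety is descriptive, OE is not itself named in the primary endpoint, and every OE result is listed. That limits the consequence but does not answer the point: a reader of the tables would not see a finding the protocol set out to look for.

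**Conclusion.** The gap is real and narrow. By the stated rules, a clinically significant lens finding dated to a compliant OE after the TE Period is left out of the TEAE tables. The exposed window is 28 post-visit days where the Week 96 or ETT Visit replaces Safety Follow-up, and 1 to 8 days with a separate Safety Follow-up after Week 96. After an ETT Visit followed by a separate Safety Follow-up, it depends on both dates (7 to 14 days for an ETT Visit on day 7).

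A reader might go on to infer that a given proportion of final OEs, or of cataracts, is lost. The documents give no OE dates, no count of subjects under 18 and no share of subjects whose visit replaces Safety Follow-up, so no such proportion can be stated. If every OE is done by its visit, nothing is lost.

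The conclusion assumes that the AE start date is the OE date and that the supplied OE window and completion definition still apply under the protocol behind the SAP. No test or decision rule changes. It is a point to consider, not a flaw in the design.

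**What to change.** In SAP 9.4.7, alongside the listing, report the number of OE-monitored subjects with a new cataract or lens-opacity finding at any OE done within the protocol window for Week 48, Week 96 or ETT. Use all OL-SS subjects under 18 at parent-study consent as the denominator. State that this count is not limited to the TE Period, since SAP 9.4 otherwise ties all safety analyses to it. Flag two groups: subjects whose OE was after the end of the TE Period, and subjects whose OE followed the start of commercial or managed-access triple combination or of another sponsor study.

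Leave the TEAE definition unchanged. Declaring all late OE findings treatment-emergent would sit badly with SAP 8.2 and 9.4.1, which exclude time spent in another sponsor study from the analysis period and flag ongoing AEs that began there as pre-treatment. Asking sites to record AEs after completion would alter the collection period in Protocol 13.1.1.3, which is a protocol change and not needed for this count.

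The cost is SAP wording and one small table from OE dates and results that the study already generates. Medication review also ends at completion, so the start date of commercial supply may be missing. In that case, flag any OE after a visit that replaced Safety Follow-up because of a transition. The downside is that a few flagged findings may have arisen after study drug; the flags let the reader see which.

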9.5 Safety Supportive Analysis

9.5.1 Adverse Events of Special Interest

For this study, elevated transaminases events and rash events, as determined by MedDRA Preferred Terms in Appendix F, are considered as adverse events of special interest.

For treatment-emergent elevated transaminases events and rash events, the following categories will be summarized for overall (“Any ELX/TEZ/IVA”):

- Subjects with events
- Subjects with events by maximum severity
- Subjects with events leading to treatment discontinuation
- Subjects with events leading to treatment interruption
- Subjects with serious events
- Subjects with related serious events
- Subjects with events leading to death
- Duration of events
- Time-to-onset of first event (with the first dose date of TC in the OLS as the reference while calculating time-to-onset)

In addition, for treatment-emergent rash events, the above categories will be summarized for the following subgroups:

- Sex (male, female)
- Female subjects with concomitant hormonal therapy (Yes, No)

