12.3 Statistical Analysis

12.3.1 General Considerations

Continuous variables will be summarized using the following descriptive summary statistics: the number of subjects (n), mean, SD, median, minimum value (min), and maximum value (max). The precision of the measurement for each continuous variable will be specified in the SAP. Unless otherwise specified, min and max values will be reported with the same precision as

the units of the raw data. The mean, median, and SD will be reported to 1 additional decimal place. Any values that require a transformation to standard units (metric or SI) will be converted with the appropriate precision.

Categorical variables will be summarized using counts and percentages. Percentages will be presented to 1 decimal place.

The baseline value, unless otherwise specified, for the long-term safety analysis will be the most recent non-missing measurement (scheduled or unscheduled) collected before the first dose of VX-445/TEZ/IVA either in the parent study or the open-label study, as applicable. The baseline value for the long-term efficacy analysis will be defined as the most recent non-missing measurement (scheduled or unscheduled) collected before the first dose of study drug in the parent study. For assessments collected in duplicate or triplicate, the baseline will be defined as the average of non-missing values.

Baseline characteristics of subjects in the open-label study will be the same as the baseline characteristics in the parent study.

Change (absolute change) from baseline will be calculated as post-baseline value - baseline value.

The **Efficacy Analysis Period** in the open-label study will include the time from the first dose of study drug in the open-label study to the last scheduled efficacy visit in the open-label study, unless otherwise specified.

The **Treatment-emergent (TE) Period** in the open-label study will include the time from the first dose of study drug in the open-label study to 28 days after the last dose of the study drug in the open-label study or to the completion date of study participation (as defined in Section 9.1.5), whichever occurs first.

The long-term efficacy analysis will be performed by parent study for the Efficacy Analysis Period in the open-label study.

In general, long-term safety analyses will be performed in a pooled fashion.

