9 STATISTICAL ANALYSIS

9.1 General Considerations

The precision standards for reporting safety and efficacy variables are provided in an internal Biometrics document that specifies the programming rules including the precision for derived variables.

Data will be summarized by treatment group in the parent study (“Control in 445-104” and “ELX/TEZ/IVA in 445-104”) and overall (“Any ELX/TEZ/IVA”).

Continuous variables will be summarized using the following descriptive summary statistics: the number of subjects (n), mean, standard deviation (SD), median, minimum value (min), and maximum value (max).

Categorical variables will be summarized using counts and percentages. Percentages will be presented to 1 decimal place.

Baseline value for clinical laboratory values, standard 12-lead ECGs, vital signs, and pulse oximetry will be the TC safety baseline defined as the most recent non-missing measurement (scheduled or unscheduled) collected before the first dose of study drug in the parent study (if the subject actually received at least one dose of ELX/TEZ/IVA during the parent study) or the first dose of study drug in the OLS (if the subject did not actually receive at least one dose of ELX/TEZ/IVA during the parent study). **Baseline value** for efficacy analyses, demographics, and baseline characteristics will be the parent study baseline defined as the most recent non missing measurement (scheduled or unscheduled) collected before the first dose of study drug in the Treatment Period of the parent study.

Change (absolute change) from baseline will be calculated as post-baseline value – baseline value. **Relative change** from baseline will be calculated as (post-baseline value – baseline value)/baseline value.

Unscheduled visits: Unscheduled visit measurements will be included in analysis as follows:

- 1) In scheduled visit windows per specified visit windowing rules
- 2) In the derivation of baseline
- 3) In the derivation of maximum and minimum values during TE period for Part A, and maximum and minimum change from baseline values during TE period for Part A for the long-term safety analyses
- 4) In individual subject data listings as appropriate

Visit windowing rules: The analysis visit windows for protocol-defined visits are provided in Section 12.1.

Incomplete/missing data will not be imputed, unless specified otherwise.

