9.4 Safety Analysis

The primary objective of the study is the evaluation of long-term safety and tolerability of TC. All safety analyses will be based on the TE Period for Part A in the OLS for subjects in the OLS for Part A. The overall long-term safety profile of study drug will be assessed in terms of the following safety and tolerability endpoints:

- Treatment-emergent adverse events (TEAEs)
- Clinical laboratory values
- ECGs
- Vital signs
- Pulse oximetry

The TC safety baseline will be used to calculate change from baseline for continuous safety endpoints.

Only descriptive analysis of safety will be performed, and no statistical testing will be performed.

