9.4.2 Clinical Laboratory Assessments

For the treatment-emergent laboratory assessments, the observed values and change from baseline values of the continuous hematology, coagulation, and chemistry results will be summarized in SI units for overall (“Any ELX/TEZ/IVA”) at each visit during the TE period for Part A for the OLS.

The number and percentage of subjects with test values meeting at least 1 threshold analysis criterion event during the TE period for Part A for the OL-SS for Part A will be summarized for overall (“Any ELX/TEZ/IVA”). The threshold analysis criterion shift from baseline will also be summarized for selected laboratory parameters. The threshold analysis criteria are provided in Section 12.4.

Results of positive urine/serum pregnancy test will be listed in individual subject data listings only. For positive serum pregnancy listing, subjects with serum HCG which are abnormally high will be selected.

In addition, a listing containing individual subject hematology, chemistry, coagulation and urinalysis values will be provided. This listing will include data from both scheduled and unscheduled visits.

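### The pooled AESI time-to-onset row in SAP 9.5.1 mixes time since starting ELX/TEZ/IVA with time since rollover; parent-group columns would separate the two

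*SAP*

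**What the plan says.** SAP 9.5.1 names two kinds of event of special interest, elevated transaminases and rash. For treatment-emergent events of either kind, "the following categories will be summarized for overall", that is, in the single column Any ELX/TEZ/IVA. One of the categories is "Time-to-onset of first event (with the first dose date of TC in the OLS as the reference while calculating time-to-onset"). Rash is also broken down by sex and, in females, by hormonal therapy. Neither kind of event is broken down by parent-study treatment group.

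The surrounding text is as follows.

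- SAP 9.1, general display rule: "Data will be summarized by treatment group in the parent study" (Control in 445-104; ELX/TEZ/IVA in 445-104) and overall.
- SAP 9.1, TC safety baseline: two kinds of subject are recognized. The baseline precedes the first parent-study dose "if the subject actually received at least one dose of ELX/TEZ/IVA during the parent study", and otherwise precedes the first open-label dose.
- Protocol 12.3.1: "In general, long-term safety analyses will be performed in a pooled fashion". Protocol 12.3.4 repeats this.
- SAP 9.4.1: a treatment-emergent event is one that is new or worse during the Part A treatment-emergent period of the open-label study. Events confined to Study 104 are not counted.
- SAP 9.2.5: exposure runs from the first open-label dose and is shown by parent group and overall.

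**The concern.** All subjects are on TC in this study, but they do not all start it here. For a former control, the first open-label dose of TC is the first dose of TC. For a subject who took TC in Study 104, it is a continuation dose. A pooled minimum, median or maximum of time to onset therefore combines a time since starting treatment with a time since changing study.

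For rash and raised transaminases, a reader will naturally want to know how soon after starting TC they appear. Former controls can answer that within this study, subject to one caveat: SAP 9.2.2 lists IVA and TEZ/IVA comparator groups, so they may already have taken components of the combination. The planned table does not show them separately. What is at stake is the interpretation of one descriptive row. No test, sample size or primary conclusion depends on it.

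**Working it through.** The plan gives no figure for AESI onset, so there is none to reproduce. The point follows from an identity; the numbers after it are illustrations.

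**Identity.** Let u be the time from first open-label TC dose to onset, and D the interval from first parent-study TC dose to first open-label dose.

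- No TC in Study 104: time since first TC dose = u.
- TC in Study 104: time since first TC dose = u + D.

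The documents do not give D. If D is assumed to be 4, 8 or 24 weeks, the two scales differ by 7 × D = 28, 56 or 168 days. An event on open-label Day 15 (u = 2 weeks) is at TC week 2 in a former control, but at TC week 6, 10 or 26 in a subject continuing TC.

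**Illustration 1: constant hazard.** Assume 0.001 per week over the 96 weeks of treatment.

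- Incidence = 1 − exp(−0.096) = 9.15%.
- Median onset among subjects with an event = −ln(1 − 0.0915/2)/0.001 = 46.8 weeks on the open-label clock, in both groups and pooled.
- In prior-TC subjects that corresponds to 46.8 + D = 50.8, 54.8 or 70.8 weeks since first TC dose for D = 4, 8 or 24.

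The pooled figure misrepresents neither group on the open-label clock, but it still has two meanings.

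**Illustration 2: early risk.** Assume 0.01 per week for the first 8 weeks on TC and 0.001 per week after that, D = 8 weeks with no gap in dosing, and a 1:1 split.

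- Former controls: cumulative hazard = 0.08 + 0.088 = 0.168; incidence = 1 − exp(−0.168) = 15.5%. The median solves 1 − exp(−[0.08 + 0.001(u − 8)]) = 0.0773, giving u = 8.5 weeks.
- Prior-TC subjects: the early period is over, so the median is 46.8 weeks, as in illustration 1.
- Pooled: 28.2 weeks, which describes neither group. With 40% or 60% of subjects on prior TC it is 24.3 or 32.0 weeks.

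**Would re-anchoring alone help?** With the same assumptions, timing everyone from first TC dose but keeping one column gives a pooled median of 32.3 weeks, still a mixture. The columns do the separating.

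**Precision by group.** SAP 6.2 expects about 250 subjects. Assume 125 per group.

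- Incidence of 5%, 9.15% or 15% gives 6.25, 11.4 or 18.75 subjects with an event, that is, about 6, 11 or 19.
- Exact 95% CI: 11/125 (8.8%), 4.5% to 15.2%; 22/250 pooled (8.8%), 5.6% to 13.0%.
- For a median from 11 onsets, the 3rd to 9th ordered values cover 93.5%, so an interval of at least 95% needs the 2nd to 10th: 1 − 2 × (1 + 11)/2048 = 98.8%.

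**The case against.** The strongest reply is that the row is disclosed, internally consistent and within the protocol. Its reference date is written out. The open-label origin is the one used for treatment-emergent events (Protocol 12.3.4.1, SAP 9.4.1), exposure (SAP 9.2.5) and the visit windows (SAP Table 12-1). The protocol asks for pooled long-term safety analyses, and SAP 9.4.1 lists every adverse event by subject. All of that stands, and it limits the point to one of presentation. It does not remove the two meanings of the row, and a listing is not a summary. The pooling rule is also stated as general, and adding columns leaves the pooled one in place.

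A reader might infer three stronger claims that the documents do not support.

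- *That the row contradicts the safety baseline.* Protocol 12.3.1 takes the baseline from data "collected before the first dose of VX-445/TEZ/IVA either in the parent study or the open-label study, as applicable", and SAP 9.4 says: "The TC safety baseline will be used to calculate change from baseline for continuous safety endpoints". But a baseline fixes which value is subtracted; it does not set a clock. Laboratory results are also placed in visits counted from open-label Day 1, so a raised ALT and the related AESI are timed alike.
- *That pooled AESI incidence is wrong or diluted.* It is a valid incidence of events emerging in the open-label study. Whether it differs from incidence in subjects new to TC depends on how the hazard changes over time, which is not known. Under a constant hazard there is no difference.
- *That an extra onset row from first TC dose would solve the problem.* For prior-TC subjects, Study 104 events are not counted, so no onset on that scale could be shorter than D, and the first event counted may not be the first on TC. The row would be roughly the open-label row plus D.

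**Conclusion.** The point holds as a minor improvement. It follows from the text of SAP 9.5.1 and 9.1 that the single onset row combines two time scales, and this needs no assumption. The size of any distortion cannot be stated: D, the group split and the hazards are all assumed above. Depending on the hazard, the open-label group medians may be equal (46.8 weeks in both) or far apart (8.5 and 46.8 weeks); the early-risk pattern behind the second case has no support in the documents and only shows what could happen. With by-group columns, the table would show time from starting TC in former controls. For prior-TC subjects it would still show only time from rollover.

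**What to change.** Keep the overall column. Add the SAP 9.1 columns, Control in 445-104 and ELX/TEZ/IVA in 445-104, to the AESI summary, including the onset row, and report n, minimum, median and maximum there. Add a footnote saying that:

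- onset in the Control column is time since first TC dose;
- onset in the ELX/TEZ/IVA column is time since rollover and excludes Study 104 events;
- any subject whose actual TC exposure in Study 104 differs from the assigned group is flagged.

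No onset row from first TC dose is needed.

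The cost is two columns and a footnote. Parent treatment group is already a display variable, and actual TC receipt in Study 104 is already needed for the TC safety baseline. The drawback is that events per group will be few, so by-group medians will be rough and should be read descriptively.
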